Patients will be evaluated at each study visit for the duration of their participation in the study. The safety plan is described in detail later in the protocol.

COMPLIANCE WITH LAWS AND REGULATIONS

This study will be conducted in accordance with current U.S. Food and Drug Administration (FDA) Good Clinical Practices (GCPs), and local ethical and legal requirements.

MATERIALS AND METHODS

SUBJECTS

Subject Selection

Participants will be recruited at the Johns Hopkins MS Center. We will recruit 10 patients with relapsing MS who are naïve to DMTs or have been on injectable DMTs (interferons or glatiramer acetate) or have been off of natalizumab, fingolimod or dimethyl fumarate for at least three months and have at least one Gd-enhancing lesions on the brain and/or spinal cord MRI on a scan obtained in three months prior to enrollment OR have at least one new T2/FLAIR lesion on the brain or spinal cord MRI done in three months prior to enrollment (compared to a previous MRI performed within 18 months of the most recent MRI).

We plan to enroll participants who have active disease, as the absence of disease activity in the followup period in these patients would be more meaningful.

Inclusion and exclusion Criteria

Inclusion and exclusion criteria
Inclusion criterion
Diagnosis of RRMS based on revised McDonald criteria
At least one Gd-enhancing lesions on the brain or spinal cord MRI done in the prior three months OR at least one new T2/FLAIR lesion on the brain or spinal cord MRI done in the prior three months (compared to a prior MRI performed within 18 months of the most recent MRI) Age>=18
Naïve to DMT or at least off these DMTs (natalizumab, fingolimod, DMF) for three months or on an injectable DMT (interferons or glatiramer acetate)
Expanded Disability Status Scale (EDSS) score at the time of screening =<3
A negative urine or serum pregnancy test must be available for premenopausal women and for women <12 months after the onset of menopause, unless they have undergone surgical sterilization
Women of childbearing potential must agree to remain abstinent (refrain from heterosexual intercourse) or use one method of contraception with a failure rate of <1% per year or a barrier method supplemented with spermicide. Contraception must continue for the duration of study treatment and for at least 24 weeks after the last dose of study treatment ^{\$\$}

Exclusion criterion
Contraindication to treatment with anti-CD20 antibodies,

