Protocol-specified therapy may be discontinued for any of the following reasons:

- Unacceptable toxicity
- Patient election to discontinue therapy (for any reason)
- Physician's judgment

SUBJECT DISCONTINUATION

Treatment stop rules: Stopping the study is equivalent to restarting the B-cell depleting antibody (i.e. ocrelizumab) or another DMT, if there is medical contraindication to the continued use of ocrelizumab (e.g. development of allergic or severe infusion reactions during the last infusion). The followings are the criteria for restarting the DMT (stopping the study).

1. A clinical relapse, affecting optic nerves (with worst visual acuity of 20/50 or less) or causing motor weakness, ataxia, bladder or bowel symptoms. Pseudo-relapses are not uncommon among patients with MS. When in doubt, the PI will use MRI to confirm development of new lesions corresponding to patient's symptoms (based on the possible localization of the symptoms).

2. Development of two new T2 hyperintense lesions or two gadolinium enhancing lesions on any MRI after the baseline MRI. The baseline MRI was defined the MRI that is obtained after three months subsequent to the first ocrelizumab infusion.

Termination rule

If four patients during the study required retreatment with ocrelizumab (or another DMT), we will terminate the study (i.e. will offer all participants the choice to resume their DMT).

STUDY DISCONTINUATION

Genentech Study Center, and the Principal Investigator has the right to terminate this study at any time. Reasons for terminating the study may include the following:

• The incidence or severity of adverse events in this or other studies indicates a potential health hazard to subjects

- Subject enrollment is unsatisfactory
- Data recording are inaccurate or incomplete
- Study protocol not followed

STATISTICAL METHODS

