We will describe the demographic, clinical characteristics and MRI data of all participants before treatment with the B-cell depleting agent. Using paired t-tests, we will compare the frequency of autoreactive mature naïve B-cells, Treg and Tfh cells and cytokine production before treatment with ocrelizumab and after the B-cell repopulation. We will report the proportion of participants who experience the return of the disease activity and the time to failure event, using a Kaplan-Meyer curve. Proportion of patients with clinical relapse, new MRI activity or disability progression will separately be reported. Quality of life data will be analyzed using linear mixed effect models.

To look at the association between long-term response to B-cell depletion therapy and autoreactivity of B-cells at different stages of development, we will use logistic regression and Cox proportional hazards models with failure or time-to-failure event as the outcome variable and the above-mentioned proportion of auto-reactive B-cells at different stages of development and the change in proportions before and after treatment as the predictor variables. Failure event as defined by the return of disease activity after the third month post-first-infusion, objectively demonstrated by development of new T2 hyperintense lesions or Gd-enhancing lesions on the MRI or a clinical relapse that is confirmed with an objective change in the neurological examination or a corresponding new or enhancing lesion on the MRI that is obtained after the onset of symptoms.

Missing Data

Because of the small sample size and close follow-up, we do not expect to encounter missing data problem. Also, each participant will be his/her own control and no between-patient comparison will be made.

Determination of Sample Size

Patients' numbers are also based on our previous studies of central and peripheral B-cell checkpoints in patients with autoimmune diseases and healthy control subjects in which we had found that the frequency of autoreactive mature naïve B-cells was 48.9±3.06% in patients and 20.1±0.9% in healthy donors. Assuming that the frequency of autoreactive cells among post-treatment repopulated B-cells will be similar to normal controls, our proposed sample size of 10 subjects per group before and after

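### The component failure proportions and the yes/no logistic model have no time horizon, so participants whose untreated follow-up ends early would count as failure-free

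*Combined protocol and SAP*

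**What the plan says.** Under Statistical Methods, the failure summary reads "We will report the proportion of participants who experience the return of the disease activity and the time to failure event", and the sentence goes on to a survival curve: "the time to failure event, using a Kaplan-Meyer curve". The components follow: "Proportion of patients with clinical relapse, new MRI activity or disability progression will separately be reported". For the link with B-cell autoreactivity, "we will use logistic regression and Cox proportional hazards models with failure or time-to-failure event as the outcome variable".

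No month is attached to any proportion or to the yes/no outcome, and no censoring rule is given. The Missing Data paragraph expects no problem.

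Subject Discontinuation treats stopping the study as equivalent to restarting ocrelizumab or another DMT. Its termination rule takes effect when four patients need retreatment, and is explained as meaning that the study "will offer all participants the choice to resume their DMT".

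**The concern.** A simple proportion and a yes/no outcome are interpretable only when everyone is observed for the same time. Here untreated observation can end early for a person who is retreated, and for the whole group once four people have been. Someone in month 14 with no event at that point has not been shown to be failure-free at month 30, but would be counted that way.

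The component proportions have a further form of the problem. A person retreated for MRI activity, who then has no relapse on treatment, enters the relapse proportion as relapse-free.

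At stake is an understated rate of return of disease activity after stopping ocrelizumab. That is a secondary outcome, but it is the clinical result that readers will look for. The logistic model would also label some unobserved failures as successes.

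**Working it through.** **Plan's own figure.** The documents give no expected failure rate or event count. The only design figure is power above 90% for the before/after B-cell comparison. It reproduces (essentially 100% if the ± values are SDs; at least 99.6% if they are SEMs from an assumed 10 to 30 subjects) but does not bear on this point.

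**Inputs from the documents**
- Sample size: "We will recruit 10 patients with relapsing MS" (Subject Selection).
- Brain MRI at months 12, 18, 24 and 30, after the month 3 baseline (schedule of events).
- Failure, from month 3: "development of new T2 hyperintense lesions or Gd-enhancing lesions on the MRI", with no minimum number, or a confirmed relapse.
- Retreatment: two new T2 or two enhancing lesions, or one of the listed relapse types. This is narrower than failure.
- Termination: four retreated patients.

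**Assumed, not in the documents:** the accrual period, the true failure rate, the share of failures that are retreated, and that all follow-up ends at termination.

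**Step 1. Can the rule plausibly be reached?** If every failure is retreated, P(X ≥ 4) = 1 − Σ(j=0..3) C(10,j) p^j (1−p)^(10−j). This is 12%, 62%, 95% and 99.9% for p = 20%, 40%, 60% and 80%.

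**Step 2. The mechanism by hand.** Suppose four failures are found at month 12 and k of the other six participants are censored before month 12. The crude proportion is 4/10 = 40% whatever k is. Kaplan-Meier at month 12 gives 4/(10 − k): 44% for k = 1, 57% for k = 3, 80% for k = 5.

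**Step 3. Average size.** Simulation of 4,000 trials per setting: enrolment over 12 months, constant hazard from month 3, detection at the next scheduled brain MRI, everyone censored at the fourth retreatment. Ranges show the spread across independent runs.

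| True failure by month 30 | Share of failures retreated | Crude proportion | Kaplan-Meier, month 30 |
|---|---|---|---|
| 50% | all | 37–38% | 53% |
| 70% | all | 39–40% | 62–63% |
| 90% | all | 39–40% | 72% |
| 50% | 60% | 46% | 51–52% |
| 70% | 60% | 58% | 69–70% |
| 90% | 60% | 63–64% | 81% |

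At 35% true failure the crude proportion is 31–34% and Kaplan-Meier 36–39%, across both shares. At 70%, about 2.6 of 10 participants (60% retreated) to 5.9 of 10 (all retreated) are early-censored non-failures.

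**Step 4. Sensitivity**
- A second simulation used a constant risk per visit, half of failures qualifying for retreatment when first detected, and accrual over 12 to 24 months. At 60% true failure, crude is 53% and Kaplan-Meier 61–62%. At 40%, they are 39% and 41%.
- With simultaneous entry, crude and Kaplan-Meier at month 30 coincide, because everyone is censored at the same point. At 70% true failure with all retreated, both are 48%.

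**Step 5. A restricted binary outcome.** One could keep only those who failed by month 24 or were followed to month 24. Under the Step 3 hazard, true month-24 failure is 1 − (1 − 0.70)^(21/27) = 61%, or 1 − (1 − 0.50)^(21/27) = 42%. With all failures retreated, the restricted proportion averages 90% and 63%, so it overshoots by 29 and 21 points.

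**The case against.** **The right methods are already planned.** The Kaplan-Meier curve stands in the same sentence as the overall proportion, and Cox stands beside logistic regression. This carries weight: the overall proportion may well be meant to come from the curve. It does not cover the component proportions, and two association models remain with no stated preference.

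**A reader might infer that the rule holds reported failure near 40%.** The documents do not support that. The limit of four in ten applies to retreated patients, and a single new lesion or an unlisted relapse type is a failure without being a retreatment trigger. The 40% figure needs every failure to be retreated, failures to be detected one at a time, and observation to end at the fourth. In the half-retreated simulation with accrual over 12 to 24 months, the crude proportion exceeded 40% in 62–86% of terminated trials at true rates of 40–80%.

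**Follow-up is not said to stop at termination.** Correct: participants are offered a choice, and those who decline could be followed. Full censoring is therefore the upper end. But event-free time after resuming a DMT says nothing about stopping treatment, and the plan does not say how to handle it.

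**Other sources of unequal follow-up are thin.** The clause on a patient electing to stop concerns protocol therapy, whose last infusion is at month 6; it is not a rule on leaving follow-up. No accrual schedule is given, and staggered entry alone does not shorten a 30-month schedule per patient. It matters only through termination in calendar time.

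**Attenuation of the logistic association was not shown.** This stands. The simulations contain no predictor. Models using the before/after change need the month 18 or 24 sample. At 70% true failure with all retreated, about 3.7 of the 5.8 early-censored non-failures are censored before month 18 and could not enter them. The mislabelling applies mainly to baseline predictors.

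**Kaplan-Meier is only a partial cure.** In the all-retreated setting nobody is at risk at month 30 in 58% of simulated trials at 50% true failure, and in 91% at 70%. This stands as a limit on the remedy.

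**Conclusion.** The point holds in a bounded form. The component proportions and the yes/no model lack a horizon and ignore follow-up time, while the plan's own retreatment and termination rules can end untreated follow-up early. Followed as written, they understate failure when termination comes early.

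At 70% true failure the crude shortfall is about 70 − 40 = 30 points if all failures are retreated and 70 − 58 = 12 points if 60% are. Both figures assume 12-month accrual and follow-up ending at termination. At 35% true failure the shortfall is 1 to 4 points (35 − 34, 35 − 31). With simultaneous entry Kaplan-Meier offers no gain at month 30.

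Kaplan-Meier is closer on average at high failure rates but not exact: it runs slightly high at 50% (53%) and falls short at 90% (72%) when all failures are retreated. With ten participants everything is imprecise; 4/10 has an exact 95% interval of 12% to 74%. The matter concerns secondary analyses and leaves the primary B-cell comparison untouched. It should be corrected, and the correction is inexpensive.

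**What to change.** - Define the failure proportion as the Kaplan-Meier estimate at a stated month, with confidence interval and number at risk, not extended beyond the last time at which anyone is at risk. Month 24 is a reasonable choice: EDSS change must be confirmed six months later, and 24 + 6 = 30 is the last scheduled visit.
- Report relapse, MRI activity and disability progression as cumulative incidence at that same month.
- State the censoring rule: at DMT resumption, withdrawal or end of follow-up. Say whether those who decline a DMT after termination stay under observation. Acknowledge that censoring one component at retreatment for another may be informative.
- Drop the logistic regression of failure and use the planned Cox model for the association.
- Raw counts may be shown with follow-up time, but after an early termination not as the 30-month failure rate.
- Do not substitute a binary outcome restricted to those who failed or were followed to month 24; Step 5 shows that it overstates failure.

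**Cost.** Only analysis wording changes. The reported figure may be less favourable and its interval wider. After an early termination, Kaplan-Meier will still understate very high failure, and month 24 itself may be out of reach. No analysis wording can recover follow-up that was not observed.

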Screening visit: PI or designee will explain the study consent to study participants, and the study visit assessments will occur after the study participants sign the consent form. Screening visit procedures include review of eligibility criteria, physical exam, EDSS, collecting vitals, and blood draw (for collecting PBMCs), and completion of Neuro-QoL adult item banks. Study participants will be enrolled into the study after the study physician confirms participants' eligibility to move forward with the study.

RATIONALE FOR STUDY DESIGN

The reason we chose a single arm, open label study, as opposed to a blinded controlled study is because the latter does not help with answering our research question. Our research question is if two courses of treatment with anti-CD20 antibody, ocrelizumab corrects the B-cell tolerance defect seen in patients with relapsing-remitting multiple sclerosis.

OUTCOME MEASURES PRIMARY OUTCOME MEASURE

Assessment of T and B-cell phenotypes and function at baseline and 18-24 months post-B-cell depletion:

The assessment T and B-cell phenotypes and function and analysis of the central and peripheral B-cell tolerance checkpoints, as well as measurement of cytokines will be done at [name] at Johns Hopkins University. 50 milliliters of blood will be drawn from participants before start of the treatment with ocrelizumab (at the screening visit) and 12 or 18 months after the second course of ocrelizumab infusion (month 18 or 24 of the study) and will be sent to [name] for the analyses explained below. We will investigate the T and B-cell phenotypes in fresh blood samples from 10 individuals with MS pre-treatment and after they repopulate their peripheral B-cells likely at either 18 or 24 months' time points. We will follow the frequencies of CD3+CD4+CD25hiCD127loFOXP3+ Tregs, circulating CD3+CD4+CXCR5+PD-1+ Tfh cells increased in several autoimmune diseases, and other CD4+ and CD8+ naïve and memory T cell subpopulations. We will also assess the production of several cytokines including IL-10, IL-17, and IFN-gamma by Tregs and other T cell subsets after activating PBMCs with phorbol-12-myristate-13-acetate (PMA) and ionomycin for 4 hours in the presence of GolgiStop (BD

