Signed, IRB approved informed consent will be obtained from patients prior to the pretreatment assessments. We will ensure that informed consent will be obtained for any mandated testing or screening process for this protocol.

Screening visit: PI or designee will explain the study consent to study participants, and the study visit assessments will occur after the study participants sign the consent form. Screening visit procedures include review of eligibility criteria, physical exam, neurological examination, collecting vitals, blood work for assessing eligibility (liver function tests, complete blood count, Hepatitis- B surface antigen, Hepatitis-B core antibody, HIV antibody, lymphocyte subset including CD19+ B-cells, total IgG and IgM and urine pregnancy test) and blood draw (for collecting PBMCs), and completion of Neuro-QoL adult item banks. Study participants will be enrolled into the study after the study physician confirms participants' eligibility to move forward with the study.

Obtaining the B-cell depleting antibody (ocrelizumab) and all the subsequent study visits and MRIs are part of routine and standard clinical care. If the B-cell depleting medication is not approved by the participants' insurance policy, the patient will be excluded from the

MRI procedures: MRI scans will be performed as part of the standard of care. Conventional T2/FLAIR/T1-weighted images as well as post-contrast T1-weighted images of the brain will be obtained at months 3 (baseline), 12, 18, 24 and 30. Conventional T2/STIR/T1-weighted images as well as post-contrast T1-weighted images of the cervical and thoracic spinal cord will be obtained at months 3 (baseline), 12 and 24. Similar to the standard of care, brain, cervical or thoracic spine MRIs may be done as needed if the patient develop symptoms that could be suggestive for an MS relapse (based on the evaluation by a study neurologist). The MRI scans will be read by an attending radiologist at Johns Hopkins University, and these readings will be used for making decisions regarding the presence of new T2 or Gd-enhancing lesions suggestive for re-emergence of the radiological disease activity.

Assessments during Treatment

procedures in bold font are standard of care.

Tests and assessments	Screeni ng visit	Infusion visits (month 0)	Month 3 (baselin e)	Month 6	Month 12	Month 18	Month 24	Month 30
Informed Consent	x							
Verifying eligibility	x							
Medical history	x		X	х	x	x	x	x

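### Post-treatment autoreactivity and its change, measured at month 18 or 24, are used to explain failures counted from month 3, so the planned association is biased if failure or retreatment alters the later value

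*Combined protocol and SAP*

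**What the plan says.** All references are to the combined protocol and SAP.

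- **Statistical Methods.** The link between long-term response and B-cell autoreactivity is to be examined by logistic regression and Cox models, with "the above-mentioned proportion of auto-reactive B-cells at different stages of development and the change in proportions before and after treatment as the predictor variables". The same section sets the outcome: "Failure event as defined by the return of disease activity after the third month post-first-infusion". New T2 or enhancing lesions, or an objectively confirmed relapse, count as failure, and no minimum of two lesions is stated.
- **Primary Outcome Measure.** Blood is drawn at screening and again "12 or 18 months after the second course of ocrelizumab infusion (month 18 or 24 of the study"). Patients are to be sampled "pre-treatment and after they repopulate their peripheral B-cells likely at either 18 or 24" months.
- **MRI procedures.** Conventional and post-contrast "images of the brain will be obtained at months 3 (baseline), 12, 18, 24 and 30".
- **Treatment stop rules.** "Stopping the study is equivalent to restarting the B-cell depleting antibody" or another disease-modifying therapy. Certain relapses qualify; the MRI trigger is "Development of two new T2 hyperintense lesions or two gadolinium enhancing lesions on any MRI after the baseline MRI". The text does not say whether a retreated patient still gives the later sample.
- **Paired tests.** Values are compared "before treatment with ocrelizumab and after the B-cell repopulation".
- **Missing Data.** No missing-data problem is expected, and the text says patients will not be compared with one another.

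**The concern.** A covariate known only at month 18 or 24 is entered as an ordinary predictor of events that may have happened up to 15 or 21 months before it was measured. A patient who fails before the draw falls into one of three groups:

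(a) no later sample;
(b) a sample taken after retreatment, when B-cells may have been depleted again and not yet repopulated;
(c) a sample taken after an untreated failure. One new lesion, for example, is a failure under Statistical Methods but is below the two-lesion MRI restart rule.

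In (b) and (c) the event may have influenced the predictor rather than the reverse. The plan names no landmark, delayed entry or time-dependent covariate, and no rule for these samples.

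At stake is the expectation, under Anticipated results, that correcting the tolerance defect goes with lasting absence of disease activity. These models are the only named analysis of that link. It is not the primary objective, but retreatment or time order alone could create or hide it.

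**Working it through.** **The plan's own figure.** None is given for the association models. The stated power above 90% is for the before/after test. It is reproduced: the difference is 48.9 - 20.1 = 28.8 points, and with 3.06 read as an SD and 10 per group the power exceeds 99.9%. With 3.06 read as a standard error from an assumed 6-30 source patients, the two-sample power is 97.0% or more. It says nothing about the association.

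**Inputs from the documents.** 10 patients; clock from month 3; last brain MRI at month 30; scans at months 12, 18, 24 and 30; draw at month 18 or 24. (Anticipated results puts repopulation at 18-24 weeks. Months are used here, as in the schedule table; the two should be reconciled.)

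**Assumptions.** No failure rate is given, so the risk by month 30 is q = 20-60%. The hazard is constant from month 3 or, closer to the Background's account of the drug's effect on disease activity, begins only at month 12. MRI failures are seen at scheduled scans.

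**Step 1, time at risk before the draw.** The window is 30 - 3 = 27 months. A month 18 draw comes after 15/27 = 56% of it, a month 24 draw after 21/27 = 78%.

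**Step 2, failures seen before the draw.** h = -ln(1-q)/27 and F(t) = 1 - exp(-h(t-3)). Activity arising between one scan and the next is first seen at the later scan. So early failures are those arising by month 12 for a month 18 draw, and by month 18 for a month 24 draw. For q = 0.4, h = 0.5108/27 = 0.0189. F(12) = 0.157, which is 0.157/0.4 = 39% of failures; the chance of at least one in 10 patients is 1 - 0.843^10 = 0.82. For hazard from month 12, replace 27 by 18 and 3 by 12.

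| Draw | Hazard from | Share of failures seen earlier | Chance of at least one in 10 |
|---|---|---|---|
| 18 | month 3 | 36-44% | 53-95% |
| 24 | month 3 | 58-67% | 71-99% |
| 18 | month 12 | none at scheduled scans | only relapses or symptom-driven scans |
| 24 | month 12 | 36-44% | 53-95% |

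**Step 3, bias when there is truly no association.** Simulated Cox hazard ratio per SD, marker N(0,1), early failures shifted by an assumed 0.5-1 SD down or up:

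| Case | Month 18 draw | Month 24 draw |
|---|---|---|
| All sampled, no shift | 0.99-1.00 | 1.00-1.01 |
| All sampled, shifted, hazard from month 3 | 0.70-0.85 or 1.20-1.45 | 0.59-0.78 or 1.26-1.71 |
| Half unsampled, rest shifted, hazard from month 3 | 0.79-0.90 or 1.13-1.29 | 0.67-0.82 or 1.21-1.53 |
| All sampled, shifted, hazard from month 12 | 0.99-1.01 | 0.70-0.85 or 1.18-1.42 |

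If all early failures are unsampled, the hazard ratio is 0.98-1.04 when the truth is 1 and 1.94-2.03 when it is 2. The reason is that, at a common draw month, the complete-case risk sets are those of an analysis started at the draw. Counting only failures after the sample gives 0.98-1.01 when the truth is 1.

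**Step 4, events left after the draw.** Expected number = 10 x (q - F(draw)). With hazard from month 3, q = 0.2 and 0.6 give 10 x (0.200 - 0.117) = 0.83 and 10 x (0.600 - 0.399) = 2.01 after month 18, and 0.41 and 0.90 after month 24. With hazard from month 12 the ranges are 1.28-3.37 and 0.62-1.43. Overall this is about 0.4-3.4.

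**The case against.** The best defence is that the stop rules equate restarting treatment with stopping the study, and that sampling is meant to follow repopulation. On that reading retreated patients leave unsampled, group (b) is empty, and the Cox hazard ratio is not distorted by their absence. Group (c) then matters only if a failure below the restart threshold changes naive B-cell autoreactivity, which no section claims. If failures begin after month 12 and the draw is at month 18, scheduled scans show no early failure at all. The model carries no alpha or power claim. The termination rule (four retreated patients) also makes the 50-60% scenarios with full follow-up possible only if enough failures stay below the restart threshold.

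Much of this stands. It limits the size of the problem and makes the hazard ratios upper-end illustrations. It does not remove the mismatch: the text does not settle whether retreated patients are sampled, untreated early failures can be, and a month 24 draw remains exposed even with hazard from month 12. The statement that patients will not be compared with one another does not help, because Cox and logistic models make exactly that comparison.

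Three stronger readings are tempting and not supported:

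- **That the association must be biased, or biased towards the hypothesis.** If the values are unchanged and everyone is sampled there is no bias. If values are changed, the direction is open.
- **That missing samples alone bias the Cox result.** If all early failures are missing, the cost is lost events. A logistic model then simply describes failures after the draw.
- **That the primary before/after comparison is invalid.** The paired tests have no time-order problem, although missing or post-retreatment samples affect them too. Pre-treatment proportions are unaffected.

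**Conclusion.** The point holds, and the plan should be changed. The time-order mismatch and the absence of any rule for it are plain in the text. Whether it produces bias depends on whether failure or retreatment alters the later value, which the documents do not say. With all early failures sampled and shifted by an assumed 0.5-1 SD, a null association could appear as a hazard ratio per SD as low as 0.59 or as high as 1.71. It would be closer to 1 if some are unsampled, and there would be none for a month 18 draw if failures begin only after month 12 and are seen at scheduled scans. These figures rest on assumed failure rates, hazards and shifts and deserve moderate confidence; the existence of the flaw deserves high confidence.

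**What to change.** 1. Model failure from month 3 on pre-treatment proportions only.
2. For the post-treatment value and the change, start the clock at each patient's sampling date, among patients who are failure-free and not retreated, and count only later failures. List earlier failures, stating whether each was sampled and whether before or after retreatment. Fix in advance how to class a failure first seen on the sampling-visit MRI. For a month 18 draw with hazard from month 3 this concerns 10 x (0.1166 - 0.0717) = 0.45 to 10 x (0.399 - 0.263) = 1.36 expected patients.
3. Report the paired tests also without post-retreatment samples, with the number of missing pairs.
4. Label the association exploratory.

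The cost is analysis-plan wording, with no extra visits or samples. The price is information: with about 0.4-3.4 failures expected after the draw, the post-treatment association can only be descriptive. The chance of no later failure is 11-42% after a month 18 draw and 39-66% after a month 24 draw (hazard from month 3), or 2-25% and 21-53% (hazard from month 12). The paired tests without post-retreatment samples would have fewer pairs.
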